**February 18, 2016**

## **A. Problem Statement/ Rationale**

Extremely preterm infants are at high risk for early hemodynamic instability. Poor modulation of vascular tone, variable responses to agitation, sepsis, development of a hemodynamically significant patent ductus arteriosus (hsPDA), and other factors may contribute to fluctuations in systemic blood pressure in the first few days of life. Moreover, preterm infants are at risk for altered cerebral autoregulation with increased periods of cerebral pressure passivity, potentially leading to the development of intraventricular hemorrhage (IVH) or white matter injury. It remains unclear whether disturbances in systemic blood pressure also result in compromised end organ perfusion. Near-infrared spectroscopy (NIRS) is a non-invasive technology, well suited to bedside monitoring of regional tissue oxygenation in these infants. *This protocol will investigate the utility of early NIRS measures in identifying preterm infants at highest risk for mortality and significant neonatal CNS morbidities including IVH and periventricular leukomalacia (PVL).* The novel approach of measuring regional tissue oxygenation as an indicator of end-organ perfusion may contribute substantially to the literature as well as to clinical practice. NIRS monitoring will provide the clinician with evidence of abnormal cerebral tissue oxygenation and impaired cerebral autoregulation. *We hypothesize that abnormal NIRS measures and increased cerebral pressure passivity in extremely preterm infants in the first 96 hours of life will be associated with mortality and the development of severe CNS morbidities.*

## **B. Specific Aims**

1. Measure regional cerebral tissue oxygen saturations in the first 96 hours of life in extremely preterm infants and identify associations between NIRS measures and the following:
  - a. Mortality prior to hospital discharge
  - b. Severe CNS morbidity including IVH, ventriculomegaly, or PVL as diagnosed by cranial ultrasound in the first ten days of life.
2. Correlate the degree of cerebral pressure passivity in the first 96 hours of life as measured by simultaneous NIRS and arterial blood pressure monitoring with:
  - a. Mortality prior to hospital discharge
  - b. Development of severe CNS morbidity as defined above

## **C. Hypotheses**

1. Lower cerebral tissue oxygenation levels and more frequent fluctuations in cerebral oxygenation will be associated with:
  - a. Mortality
  - b. Severe CNS morbidity
2. Increased periods of cerebral pressure passivity will be associated with:
  - a. Mortality
  - b. Severe CNS morbidity

## **D. Background/ Previous Studies**

### **Brain Injury in prematurity**

Modern perinatal care has improved survival rates for extremely preterm infants, but there has been little to no improvement in their neurodevelopmental outcomes. Preterm infants are at risk for fluctuations in blood pressure and oxygenation. Vulnerability and immaturity of the preterm brain may further predispose these infants to developing

intraventricular hemorrhage or ensuing white matter injury with long term neurological impairment. Hypotension itself may not lead to cerebral ischemia [1] and medications used to treat hypotension have different effects on cerebral blood flow [2]. Strategies to clarify the timing of insults to the brain and thus potentially intervene before injury occurs are essential. This study will focus on the detection of cerebral oxygenation abnormalities and impairment of cerebral autoregulation, which may identify which infants are at highest risk for ensuing brain injury.

### **NIRS principles**

NIRS permits measurement of regional cerebral oxygenation. Unlike pulse oximetry, which is dependent on arterial pulsations, NIRS can effectively detect regional oxygenation during low perfusion states. It has most commonly been used to measure cerebral oxygenation, where near-infrared light is transmitted and detected by a sensor placed on an infant's forehead. Near-infrared light at different wavelengths is measured, and as oxy-hemoglobin ( $\text{HbO}_2$ ) and deoxy-hemoglobin (HHb) have different absorption spectra, regional tissue oxygen saturation ( $\text{rSO}_2$ ) can be calculated:  $\text{rSO}_2 = \text{HbO}_2 / (\text{HbO}_2 + \text{HHb})$ . This measurement is made at a depth of approximately 2.5-3 cm beneath the sensor. Assuming a weighted average of 20% arterial, 75% venous, and 5% capillary blood, the  $\text{rSO}_2$  reflects a regional balance between oxygen supply and demand similar to a mixed venous oxygen saturation of the underlying tissue. While an absolute value of  $\text{rSO}_2$  associated with tissue damage has not been standardized, an  $\text{rSO}_2 < 40\%$  during cardiac surgery may be associated with early post-operative neuropsychological dysfunction, a critical reduction in oxygen flux, EEG changes, and intracellular anaerobic metabolism and depletion of high-energy phosphates, especially when lasting longer than 10 minutes.[3-5] Hypoxia studies performed in piglets demonstrated neuronal mitochondrial injury in the hippocampal CA1 zone for cerebral  $\text{rSO}_2$  values 30% to 40% and cellular vacuolization and fragmentation for  $\text{rSO}_2 < 30\%$ .[6]

NIRS is non-invasive, requires minimal caregiver attention once properly positioned, demonstrates good reproducibility in the neonate [7], and provides a continuous signal, which is not affected by changes in blood pressure, pulse, or temperature. However, interpretation of NIRS values must be made in the context of other factors that influence cerebral blood flow and oxygenation aside from anemia, such as mean arterial blood pressure, carbon dioxide tension, glucose levels, metabolic rate, and drug administration. NIRS monitoring has increasingly been utilized in a clinical neonatal intensive care setting for preterm infants including for evaluation of patent ductus arteriosus treatment, respiratory distress syndrome, therapy for hypotension, NEC, and anemia.

### **Impairment of cerebral autoregulation**

Preterm infants are at higher risk for impaired cerebral autoregulation, which can also be readily detected using NIRS. NIRS measures of  $\text{rSO}_2$  provide a good estimate of cerebral blood flow. [8-10] This approximation has been validated in animal studies using the gold standard radioactive microsphere technique [11, 12] and confirmed by transcranial Doppler ultrasound as a reliable method to assess for impaired cerebral autoregulation. [10] Specifically, concordance between mean arterial blood pressure and  $\text{rSO}_2$  indicates a pressure passive cerebral circulation and presumed loss of autoregulation. [11, 13] The prevalence of pressure passivity has been quantified using a PPI defined as the percentage of 10-min epochs with significant coherence between mean arterial pressure (MAP) and  $\text{rSO}_2$  signals in the low frequency range. [11] A NIRS study in preterm infants found that cerebral pressure passivity signifying loss of autoregulation occurred in a majority of premature infants with a mean PPI of 20%. [11]

Pressure passivity was associated with low gestational age and birth weight, systemic hypotension, and maternal hemodynamic factors. Loss of autoregulation with concordant changes between MAP and cerebral oxygenation in preterm infants was also significantly associated with increased severe IVH and PVL [12, 14] and with mortality [15] in single center studies.

### **Neurodevelopmental outcomes in preterm infants**

Abnormal NIRS measures may be associated with poor outcomes in preterm infants. For example, decreased cerebral oxygenation and impaired cerebral autoregulation have been associated with the subsequent development of severe IVH or PVL [12, 16]. Clinical predictors currently associated with reductions in the risk of death or profound neurodevelopmental impairment include higher gestational age, exposure to antenatal steroids, female sex, singleton birth, and higher birth weight [17]. The addition of early NIRS measures to these clinical predictors may enhance a clinician's ability to counsel families regarding neurodevelopmental outcomes and the likelihood of intact survival in the preterm infant.

## **E. Methods:**

### **1. Study Design**

This multi-center, prospective observational pilot study will investigate NIRS monitoring of end organ oxygenation and cerebral autoregulation at six centers with previous NIRS experience with an estimated total enrollment of 100 infants over a one-year period. After enrollment, NIRS sensors will be applied to an infant's forehead to measure cerebral oxygenation within the first 96 hours of life. NIRS data, in addition to blood pressure and systemic oxygen saturation, will be continuously acquired until 96 hours of age or earlier if arterial access becomes unavailable. Data will be analyzed in 20-minute intervals to determine the mean cerebral oxygenation ( $rSO_2$ ) and pressure passivity index (PPI as defined below), as well as a low  $rSO_2$  index (time with  $rSO_2 < 40\%$ ). Statistical analyses will include logistic regression and longitudinal modeling to determine the association between these NIRS measures and the development of in-hospital mortality or severe neurologic morbidities as previously described.

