#### Exclusion Criteria

Lethal chromosomal abnormality, major congenital anomaly, decision not to provide full intensive care support, or skin integrity insufficient to allow placement of NIRS sensors

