#### **4. Statistical Considerations**

##### Outcomes

The primary outcome measures will be mortality before hospital discharge and severe CNS morbidity. Severe CNS injury will be documented by evidence of grade 3 or 4 IVH, ventriculomegaly, or periventricular leukomalacia as suggested by echodensity on cranial ultrasound in the first ten days of life.

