##### Sample Size Estimate

This study would be done at eight centers with an estimated total enrollment of 100 infants over a one-year period. Literature is unavailable regarding expected differences in NIRS measures for preterm infants with CNS morbidity or mortality. One hundred infants will yield 80% power at the 0.05 level of significance to detect an association between NIRS measures and morbidity-free survival if 8% of the variance in low rSO2 index can be explained by the subsequent development of CNS-morbidity or mortality. Similar effect size can be expected for the predictor variable PPI. Power may be improved by the inclusion of covariates in the full logistic regression model.

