##### Statistical Analysis

Analyses will include mixed effects regression models for repeated measures to examine the relationship between NIRS measures of low rSO2 index, PPI, and the outcome of CNS-morbidity or in-hospital mortality. Analyses will be adjusted for gestational age, birth weight, sex, center, and SNAPPE-II. Secondary analyses may look at additional NIRS measures as predictors including fractional tissue oxygen extraction (FTOE) and degree of variability in cerebral saturation levels.

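### NIRS readings taken after a brain lesion can count as its predictors: the 96 h recording lies inside the ten-day lesion window and no rule puts exposure before outcome

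*Combined protocol and SAP*

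**What the plan says.** **Exposure.** E.1 Study Design states that NIRS, blood pressure and saturation data "will be continuously acquired until 96 hours of age or earlier if arterial access becomes unavailable". E.3 forms the low rSO2 index and the pressure passivity index from all usable data; the only reduction it mentions is for missing time.

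**Outcome.** E.4 Outcomes defines severe CNS injury as grade 3 or 4 IVH, ventriculomegaly, or "periventricular leukomalacia as suggested by echodensity on cranial ultrasound in the first ten days of life". No scan schedule is given.

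**Entry.** E.2 admits infants under 24 h old. The exclusions are "Lethal chromosomal abnormality, major congenital anomaly, decision not to provide full intensive care support, or skin integrity insufficient to allow placement of NIRS sensors"; an existing lesion is not among them.

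**Analysis.** E.4 Statistical Analysis plans "mixed effects regression models for repeated measures to examine the relationship between NIRS measures" and the outcome of CNS morbidity or in-hospital death. It adjusts for gestational age, birth weight, sex, center and SNAPPE-II, with no landmark, lag or lesion-time term.

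**Intended use.** Sections B and C speak of association and correlation. Other sections go further:
- Section A will investigate the "utility of early NIRS measures in identifying preterm infants at highest risk for mortality and significant neonatal CNS morbidities".
- Section D says that strategies to "clarify the timing of insults to the brain and thus potentially intervene before injury occurs are essential".
- On counselling families, Section D adds: "The addition of early NIRS measures to these clinical predictors may enhance" a clinician's ability to do so.
- The Sample Size Estimate refers to variance in the low rSO2 index that "can be explained by the subsequent development of CNS-morbidity or mortality".

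**The concern.** The exposure window lies wholly inside the CNS outcome window. An infant who bleeds on day 1 or 2 goes on contributing readings until 96 h, and all of them enter that infant's indices. A bleed may itself change cerebral saturation and its relation to blood pressure. A positive CNS result would then be a valid association that could not show which came first.

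Intervening before injury and adding early NIRS to the predictors used in counselling both need NIRS to come first. The mixed models do not resolve this, because ordering repeated measures around a lesion requires a lesion or scan time, and the protocol does not say that scan or death times are collected.

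Mortality on its own is different. Recording always precedes death, so the only issue there is short lead time. The CNS component still enters the combined outcome used for the power statement and the main model.

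**Working it through.** **1. The plan's own figure.** Inputs from the Sample Size Estimate: N = 100, alpha 0.05 (taken as two-sided), 8% of variance explained.
- Fisher z: r = √0.08 = 0.283; power = Φ(atanh(r)·√97 − 1.96) = Φ(0.291 × 9.849 − 1.96) = Φ(0.904) = 81.7%.
- Noncentral F with f² = 0.08/0.92: 83.1%.

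The stated 80% is reproduced to within about 2 to 3 points. The ordering problem does not affect this figure.

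**2. The windows.** Ten days is 240 h, and 96/240 = 40%. The whole recording period falls in the first 40% of the lesion window. Entry (E.2), data handling (E.3) and modelling (E.4) contain no step that would put readings before the lesion.

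**3. An illustration of size.** The documents give no event rate, onset times or post-lesion shift, so every input here except N and alpha is an assumption:
- 100 infants, recording from 12 h to 96 h (84 h), and no NIRS difference before the event.
- 15 events (7 lesions, 8 deaths) or 25 events (13 lesions, 12 deaths). Deaths add no post-event readings.
- All, half or a quarter of events inside 96 h, with onset uniform on 6–72 h or 24–96 h; the rest occur later.
- Index shifted by 0.5 or 1.0 between-infant SD after lesion onset.
- Two-sided t-test at 0.05 on the per-infant mean, 10,000 replicates per cell.

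The induced standardized difference is (lesions/events) × (share inside 96 h) × shift × (mean fraction of recording after onset).
- Onset 6–72 h: the fraction is 6/66 × 1 + 60/66 × (96 − 42)/84 = 0.675.
- Onset 24–96 h: the fraction is (96 − 60)/84 = 0.429.
- Largest: 13/25 × 1 × 1.0 × 0.675 = 0.35. Smallest with all events inside: 7/15 × 1 × 0.5 × 0.429 = 0.10.
- For the largest, with 25 against 75 infants, noncentrality is 0.35 × √(25 × 75/100) = 1.52, which gives rejection of about 32%.

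**4. A fixed-age landmark under the same assumptions.** The plan's effect corresponds to d = √[(0.08/0.92)/(p(1 − p))] = 0.83, 0.74 and 0.68 at event rates p = 15%, 20% and 25%, with 83% power when nobody is excluded. If all events fall inside 96 h, a 48 h landmark keeps 24/66 = 36% (onset 6–72 h) or 48/72 = 67% (onset 24–96 h) of them.

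| Events inside 96 h | All | Half | A quarter |
|---|---|---|---|
| Induced difference, SD | 0.10–0.35 | 0.05–0.18 | 0.02–0.09 |
| Rejection, recording to 96 h | 7–32% | 5–12% | 5–7% |
| Rejection, recording ends uniformly at 48–96 h | 6–22% | 5–10% | 5–7% |
| Events kept, 48 h landmark | 36–67% | 68–83% | 84–92% |
| Power, 48 h landmark | 45–70% | 69–78% | 77–81% |
| Power, 72 h landmark | at most 45% | 57–70% | 73–78% |
| Rejection, 48 h landmark, half of earlier lesions unseen | 5–10% | 5–6% | 5% |

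Rejection here is of the hypothesis that NIRS before the lesion carries no information. If all earlier lesions are seen by 48 h, the landmark test holds its level (4.6–5.5%).

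**5. Sensitivity to the assumptions.** With a shift of only 0.25 SD, rejection in the full-recording analysis is roughly 4–7%. If instead every event is a lesion (20–30% of infants, 40–90% of lesions before 96 h, the same 0.5–1.0 SD shifts), it is about 7–62%.

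**The case against.** The strongest reply is that the planned inference is unaffected. The aims, hypotheses and methods speak of association, this is an observational pilot, and no prediction model, cut-off or accuracy analysis is planned. Much of the forward-looking wording is conditional or sits in Background. On this view a wording change and a limitation sentence would do. The point about the aims stands: the planned test is not in error, and the rejection rates above are not false positives for the association hypothesis. But Section A gives early identification as the purpose of the protocol, and the power statement describes the outcome as following the NIRS measure.

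The second reply is that the size rests on assumptions. It does: 32% comes from the most adverse cell, a small shift or few early events brings the rate close to 5%, and the per-infant mean is not the plan's adjusted repeated-measures model. However, without event times the sponsor could not tell which case applies.

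Third, applying a ten-day definition already implies knowing the age at scan at least to the day, and 20-minute NIRS intervals keep early readings separable. A landmark analysis may therefore be possible later. That is fair, but it would not be pre-specified.

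Fourth, the landmark analysis has lower power, and unscanned infants may carry undetected bleeds. Both are true, which is why it should be supplementary and reported as an estimate with an interval.

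**Conclusion.** The concern holds and should be fixed. As written, the plan lets post-lesion readings support an early-identification conclusion about CNS injury. The association analyses remain valid, and death alone is not affected by the ordering problem.

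That no ordering rule exists is clear from the text. The practical size cannot be derived from the documents. Under the assumptions listed, the rate of wrongly concluding that pre-lesion NIRS is informative runs from about the nominal 5% to 32%, and from 5% to 22% if recording stops earlier because arterial access is lost. The event rate, share of deaths, onset times and post-lesion shift drive that range, and all are assumed.

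**What to change.** In E.3 and E.4:

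1. Record the date and time of each clinically obtained cranial ultrasound and of death.
2. Keep the 96 h analysis as planned, labelled as association that may include post-lesion readings.
3. Pre-specify one supplementary landmark analysis at a fixed age chosen by the sponsor before data are seen. Use NIRS up to that age in infants alive with no qualifying lesion seen by then, count only later outcomes, and rest any predictive or early-identification statement on it.
4. Report how many infants had no scan by the landmark, and state that scan time marks detection, not onset.

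Do not truncate records at diagnosis in cases only; that would tie recording length to outcome.

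The cost is two data items and a short paragraph, with no added scans and no change to the planned analysis. The downside is power: early events and later NIRS hours drop out. The landmark powers above also assume that the effect and SD up to the landmark equal those to 96 h. A 72 h landmark would leave no events at all if every onset fell by 72 h. Earlier bleeds that were never scanned are not fully removed.

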### **3. Study Intervention/ Data Collection**

After enrollment, a NIRS neonatal sensor (Covidien) will be placed on the infant's forehead for continuous monitoring of cerebral saturation. Clinicians will be blinded to  $rSO_2$  measures by obscuring the monitor with a shield. NIRS sensors will be assessed on a daily basis to evaluate surrounding skin integrity and replaced as necessary. NIRS data in addition to continuous patient data including blood pressure and systemic oxygen

saturation will be acquired at a sampling rate of 1/30 Hz until 96 hours of life. Data will be collected using a Vital Sync bedside device allowing for data integration from the bedside monitor and INVOS. Blood pressure readings will be obtained from an indwelling arterial catheter. All data will be downloaded to media for secure electronic submission and subsequent processing by a central analyst. Data will be identified by study number only and will be maintained in a secure location. Total time with missing data will be ascertained. Of the remaining useful NIRS data, mean rSO2 and PPI (total percentage time with concordance between rSO2 and mean arterial blood pressure as determined in the very low frequency range (1/30 Hz)) will be calculated over 20 minute intervals. Concordance will be defined as a Pearson's correlation coefficient >0.5. Percentage of time with cerebral rSO2 <40% will be defined as a low rSO2 index. Blood gas pCO2 levels will be collected for possible confounding effects of hypocarbia or hypercarbia on cerebral blood flow. Perinatal data including birth weight, gestational age, sex, time of blood transfusions, use of pressors, and Score for Neonatal Acute Physiology Perinatal Extension II (SNAPPE-II) will be utilized.

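### Cerebral rSO2 recording ends when arterial access is lost, although only the pressure passivity index needs arterial pressure; recording rSO2 to 96 hours would be a cheap improvement

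*Combined protocol and SAP*

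**What the plan says.** Section E.1 (Study Design) puts NIRS, blood pressure and systemic saturation under one stop rule: they "will be continuously acquired until 96 hours of age or earlier if arterial access becomes unavailable". Section E.3 (Study Intervention/Data Collection) covers the same signals without the exception: "saturation will be acquired at a sampling rate of 1/30 Hz until 96 hours of life". It takes blood pressure from the arterial catheter and defines PPI as concordance between rSO2 and mean arterial pressure. It defines the low rSO2 index from rSO2 alone, as the share of time below 40%.

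Aim 1 in section B is to "Measure regional cerebral tissue oxygen saturations in the first 96 hours of life in extremely preterm infants" and relate the measures to death and severe CNS morbidity. Only Aim 2 calls for simultaneous arterial pressure. Hypothesis 1 in section C begins "Lower cerebral tissue oxygenation levels and more frequent fluctuations in cerebral oxygenation will be associated with", so both level and variability of rSO2 matter. The Statistical Analysis section uses the low rSO2 index and PPI as main predictors in mixed models for repeated measures. On covariates it states: "Analyses will be adjusted for gestational age, birth weight, sex, center, and SNAPPE-II".

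**The concern.** A requirement that belongs to Aim 2 cuts short the exposure for Aim 1. Once the line is out, PPI cannot be computed, but the forehead sensor could still supply mean rSO2, the low rSO2 index and rSO2 variability. No section says why rSO2 should stop as well.

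Hours that are not recorded cannot be recovered, and a time term in the model cannot replace them. The later part of the 96-hour window would be observed only in infants who keep a line. The low rSO2 index is also the predictor on which the sample size rests. The Statistical Analysis section does not say how postnatal age enters the model, and no section asks for the reason that recording stopped. The data as planned would therefore not show whether early stopping was related to outcome.

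**Working it through.** **1. Which measures need the line (from the definitions in E.3 and the aims in B)**

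| Measure | Aim | Needs arterial pressure |
|---|---|---|
| Mean rSO2 | 1 | No |
| Low rSO2 index | 1 | No |
| rSO2 variability | 1 (Hypothesis 1) | No |
| PPI | 2 | Yes |

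**2. Intervals lost.** Twenty-minute intervals (E.1) give 3 per hour.
- Line lost at 48 h: (96 − 48) × 3 = 144 intervals unobserved.
- Line lost at 72 h: (96 − 72) × 3 = 72 intervals unobserved.
- A full record from birth has 96 × 3 = 288 intervals. A record starting at 24 h, the upper age limit at entry, has 72 × 3 = 216. Line loss at 48 h thus removes 144/288 = 50% or 144/216 = 67%.

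**3. The plan's own power figure.** The Sample Size Estimate states: "One hundred infants will yield 80% power at the 0.05 level of significance", for 8% of variance explained. The test and its sidedness are not given. With a two-sided Fisher z test of a correlation:
- r = √0.08 = 0.283 and atanh(r) = 0.2908.
- Power = Φ(0.2908 × √97 − 1.96) = 81.7%.

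The stated 80% is reproduced to within 2 points and is not disputed.

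**4. Effect of shorter records on power.** The documents give neither the timing of line loss nor the within-infant variability, so this step rests on an assumed model. An infant's summary is the mean of independent 4-hour blocks, with between-infant variance 1 and block SD equal to k times the between-infant SD. Its variance is 1 + k²/b for b blocks. The 8% is taken to apply to full records and is divided by the ratio of shortened to full variance.

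Recording from birth gives 24 blocks, or 12 if the line is lost at 48 h. Recording from 24 h gives 18 blocks, or 6.

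For k = 1, every line lost at 48 h:
- From birth: (1 + 1/12)/(1 + 1/24) = 1.040. R² = 0.08/1.040 = 0.0769. Power 80.1%.
- From 24 h: (1 + 1/6)/(1 + 1/18) = 1.105. R² = 0.08/1.105 = 0.0724. Power 77.5%.

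For k = 1, half the lines lost at 48 h (averaging the two variances):
- From birth: 1.0625/1.0417 = 1.020. R² = 0.0784. Power 80.9%.
- From 24 h: 1.1111/1.0556 = 1.053. R² = 0.0760. Power 79.6%.

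Sensitivity to k, every line lost at 48 h:

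| k | Power, start at birth | Power, start at 24 h |
|---|---|---|
| 0.5 | 81.3% | 80.6% |
| 1 | 80.1% | 77.5% |
| 2 | 76.1% | 68.2% |

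The 68.2% needs three things together: universal line loss at 48 h, a late start, and block SD twice the between-infant SD.

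**5. Bias.** A distorted whole-window summary requires both that line loss is related to outcome and that rSO2 changes with postnatal age. The documents state neither, so size and direction cannot be given.

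**The case against.** A reader might infer that E.1 and E.3 set rival stop rules. The text does not support that firmly. E.3 lists blood pressure among the signals taken to 96 hours and also says that it comes from the arterial catheter, so taken literally it could not be carried out after line loss. It is probably shorthand for E.1. Aim 1 names a window and does not promise a complete record. What stands is that the two sections should say the same thing.

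A common stop also has a rationale. A catheter is an entry criterion, the two main predictors are studied together, and a shared stop keeps them on the same hours. Section D (NIRS principles) adds that "interpretation of NIRS values must be made in the context of other factors that influence cerebral blood flow and oxygenation", arterial pressure and carbon dioxide tension among them, and E.3 says that pCO2 "levels will be collected for possible confounding effects of hypocarbia or hypercarbia on cerebral blood flow". This is fair but not decisive. The adjustment list in the Statistical Analysis section contains neither pressure nor pCO2, and a same-hours analysis stays available by restricting the data.

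E.1 does plan longitudinal modeling, mixed models accept records of unequal length, and E.3 ascertains total missing time. These help with analysis but do not restore unrecorded hours. It is also true that recording on would not equalize coverage: age at entry, death and the stops in section F would still vary it.

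Two further readings go too far. One is that the rule leaves the study underpowered: the sample-size statement uses a between-infant share of variance, and the loss above is small unless the assumptions are extreme. The other is that the Aim 1 results will be biased: that needs two conditions on which the documents are silent.

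**Conclusion.** The point holds as a cheap improvement. The rule in E.1 gives up recoverable Aim 1 data for a reason that applies only to Aim 2: 144 intervals for an infant whose line is lost at 48 h, 72 if it is lost at 72 h. With block SD equal to between-infant SD, power moves from 81.7% to 77.5-80.1% if all lines are lost at 48 h, and to about 79.6-80.9% if half are. Those figures rest on assumed timing, independent 4-hour blocks, and line loss unrelated to outcome. The case therefore rests on avoidable loss of a main exposure in the later hours, not on a power shortfall or a demonstrated bias.

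**What to change.** - Reconcile E.1 and E.3 so that rSO2 and systemic saturation are acquired to 96 hours of age regardless of arterial access, subject to the skin-integrity and instability provisions of section F. Only blood pressure and PPI would end at line loss.
- State in the Statistical Analysis section that postnatal hour is a term in the repeated-measures model, and that analyses combining PPI with the low rSO2 index can be restricted to hours with both signals.
- Record the reason whenever recording stops before 96 hours.

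On paper this is one protocol sentence, a model term with a short note, and one case-report field. The practical cost is longer sensor wear and more skin checks in infants without a line, with no simultaneous arterial pressure for those hours. Wear would stay within the 96 hours already planned for infants who keep a line. Section F lists skin irritation as a possible risk, notes the manufacturer's recommendation to change the sensor every 24 hours, and requires frequent monitoring. It also reports earlier four-day use of one sensor without difficulty. If the sponsor keeps the common stop, E.1 and E.3 should still be made to agree, with the reason given.
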